1.1 Study Abstract

Obesity is a major public health concern. INtensive Lifestyle Intervention (INLI) addressing diet, physical activity, and behavior change is the gold standard weight loss treatment for adults with cardiometabolic risk factors. Typical treatment involving 16-36 face-to-face sessions with a specialist produces clinically significant (5-8%) weight loss in 50-67% of obese adults with or without medical comorbidities (Diabetes Prevention Program Research Group [DPP], 2002; Look AHEAD Research Group [Look AHEAD], 2007). However, a recent comparative effectiveness trial now has demonstrated that an INLI that incorporates technology and remote coaching can produce weight loss comparable to that achieved by face-to-face intensive treatment (Appel et al., 2011). That breakthrough opens the possibility that it may be feasible to optimize treatment still further to develop more effective, resource-efficient obesity interventions than previously was believed possible.

Traditional research methods have typically treated INLIs as bundled “treatment packages,” making it difficult to assess definitively which aspects of an intervention can be reduced, eliminated, or replaced to improve efficiency. Using traditional research methods (i.e., multi-armed randomized clinical trials (RCTs) testing each new feature one at a time) would require running many studies over decades, an exorbitantly expensive process that would likely be outpaced by the development of newer technologies. This modern paradox prompts us to consider a new research methodology that may offer a quicker, more efficient way to test the effectiveness of multiple intervention components simultaneously.

1.2 Study Objective

The overall objective of the proposed research is to use an innovative methodological framework, the Multiphase Optimization Strategy (MOST) ([name] et al., 2007), to design, for the first time, an optimized, scalable version of a technology-supported INLI for obesity. MOST involves highly efficient randomized experimentation to assess the effects of individual treatment components, and thereby identify which components and component levels make important contributions to the overall program effect on weight loss. This information then guides assembly of an optimized treatment package that achieves target outcomes with least resource consumption and participant burden. Because the intervention strategies being tested minimize in-person coaching and leverage technology that participants already own, the new optimized intervention, to be called Opt-IN, will be more scalable than traditional INLIs. Opt-IN will thus enjoy greatly increased reach, and enable significant progress in the fight against obesity.

1.3 Primary Aim 1

To identify which components/component levels from five components under consideration for inclusion in Opt-IN contribute meaningfully to improvement in (a) average weight loss, and (b) percent achieving >7% weight loss among obese adults over a 6-month period. The five components to be tested will be: (1) coaching intensity (12 vs. 24 phone sessions), (2) text messaging (No vs. Yes), (3) progress report to participant's primary care provider (No vs. Yes), (4) recommendation to use meal replacements (No vs. Yes), (5) training participants' self-selected buddies to be supportive (No vs. Yes). We will use a highly efficient experimental strategy powered to detect effects of individual components as well as all two-way interactions.

1.4 Primary Aim 2

To apply the results obtained in Primary Aim 1 to build (1) an intervention made up of only active components and (2) if necessary, a second intervention that is optimized for scalability. Intervention (1) will be made up of the best set of components and component levels, based on the results of the experiment conducted in Primary Aim 1. Our conversations with private insurers suggest that in order to be scalable, Opt-IN needs to be implementable for \$500 or less. If Intervention (1) exceeds an estimated cost of \$500, we will identify the combination of components and component levels corresponding to the largest treatment effect that can be obtained for implementation costs of \$500 or less. This will be the new Opt-IN intervention.

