3.1 Primary Research Question

Which components/component levels from five components under consideration for inclusion in Opt-IN contribute meaningfully to improvement in (a) average weight loss, and (b) percent achieving $\geq 7\%$ weight loss among obese adults over a 6-month period? The five components to be tested will be: (1) coaching intensity (12 vs. 24 phone sessions), (2) text messaging (No vs. Yes), (3) progress report to participant's primary care provider (No vs. Yes), (4) recommendation to use meal replacements (No vs. Yes), (5) training participants' self-selected buddies to be supportive (No vs. Yes).

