3.2 Design Summary

The goal of the proposed study is to determine the optimal composition of a technology supported intervention for obesity that minimizes expense and burden to participants, while achieving 6 month weight loss outcomes comparable or superior to those achieved by the current full cost, full burden form of INLIs (DPP, 2002; Look AHEAD, 2007). All intervention components to be examined were selected based on the Opt-IN model's prediction that they enhance behavioral adherence to weight regulation via the designated pathways. Additionally, all components meet two criteria: (i) that their relative advantage in terms of influence on weight loss is currently unknown, and (ii) that their relative advantage in terms of cost and/or burden is clear. Components and their mechanisms are outlined in Table 1; the rationale for each component follows.

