3.3 Study Population and Eligibility Criteria

3.3.1 Source Population

Enrollees will be adults between ages 18 and 60 with BMI 25-40. At least half will be >45 years of age. They must be weight stable (no loss or gain >25 lbs for the past 6 months), not enrolled in any formal weight loss program or taking anti-obesity medications, but interested in losing weight. Candidates must own a Smartphone and be willing to install our Opt-IN app so that their data can be transmitted wirelessly to a study coach. They must be able to use the app to record dietary intake, physical activity, and weight onto the Smartphone. Prior to participating in any study procedure, they must voluntarily provide informed consent.

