Primary Aim 2 is to make decisions about intervention components and component levels based on the factorial experiment results. We propose to use a modified version of a decision making approach frequently used in engineering (Wu & Hamada, 2000), which emphasizes main effects, using interactions as additional valuable information. This emphasis is consistent with our objective of identifying a set of components and component levels in which each component is making a detectable contribution to the overall effect, and any inactive components have been eliminated. We remind the reader that the mixed model analysis will be performed using effect coding, which will keep any covariances among main effects and interactions to a minimum. This makes it reasonable to start the decision making process by examining main effects, and then to consider interactions carefully in subsequent steps in the process. (Recall that our theoretical model does not predict any substantially-sized higher-order interactions, which is the basis for selection of the highly economical fractional factorial design. This Resolution V design enables examination of all two-way interactions.) The decision making process can be summarized as follows: Step 1: Initial tentative selection of components and component levels, consisting of identification of the components that show a significant main effect on the primary outcome variable, weight. If buddy training, recommended meal replacements, texting, or PCP report have a significant main effect, they will tentatively be selected for inclusion in the intervention. If there is a significant positive main effect of Number of Phone Coaching sessions, this is evidence that the more expensive level (24 sessions) performs better than the less expensive level (12 sessions), so it should be selected; otherwise, the less expensive level should be selected. Step 2: Consideration of interactions and final decision. Next we will examine interactions to look for any indication that we should consider reversing a decision made in Step 1. For example, suppose both Texting and PCP Report have significant main effects, so they were tentatively selected in Step 1. If there is a significant negative interaction between them, this means that the combined effect of Texting and PCP Report is less than the sum of the main effects. Suppose Texting has the larger main effect of the two. In that case we will start from the premise that Texting is selected, and then pose this question: When Texting is selected, *does PCP Report have a large enough incremental effect to justify its selection?* This question can be addressed by examining the simple effect of PCP Report when Texting is at the Yes level. Similar decision making logic will be used to examine all significant interactions that involve any components selected in Step 1 to arrive at the final decisions about selection of components and component levels. Step 3: Identifying the combination of components and levels that produces the largest effect that can be obtained for \$500 or less. If the costs associated with the combination of component and component levels selected in the process described above exceeds the upper limit of \$500, it will be necessary to consider less expensive versions of the intervention. Using as a starting point the set of components and component levels selected in Step 2, we will examine various scenarios in which we remove Yes/No components and change the levels of Either/Or components, and compute the expected outcome based on the regression parameters obtained in the statistical analysis to select the one with the largest expected effect that can be delivered for under \$500.

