5.2 Sample Size and Power

We base power on our primary endpoint: weight change from baseline to the 6-month timepoint. Our interest is in identifying the intervention components that make a more than minimal contribution to average weight loss, or conversely to identify those components that have minimal or no effect on weight loss. Our operational definition of more than minimal is a component effect size of .25 (mean difference divided by standard deviation). Thus, we have powered the study to detect effects of .25 or greater. Using the standard deviation estimate of 4 kg from Amundson et al (2009), which had a follow-up time similar to ours, this translates to a 1 kg difference in weight loss; we view weight loss of less than 1 kg as a minimal effect. There are five components in our 2^{5-1} fractional factorial design. Based on the minimal detectable effect size of .25, the total sample size will be 560 subjects. Based on our previous MBC and PDA+ studies, we conservatively assume an attrition rate of 10% at the 6-month timepoint, so that there will be approximately 504 subjects at this timepoint. Thus, each of the component main effect estimates will be based on 504 subjects, that is, 252 subjects in each of the two levels of the component. Based on these assumptions, we can detect a main effect or interaction effect size of .25 for each component with 80% power under a two-tailed hypothesis test.

Based on our current enrollment as of January 2017, approximately 45% of consented participants were eligible to be randomized after screening. We estimate that we will need to consent approximately 1250 subjects in order to obtain 560 eligible participants for randomization. Of the 560 eligible participants randomized, all will be asked to find a "Buddy" to participate in the study. We are estimating that approximately 850 "Buddies" will need to be verbally consented. (1250 participants + 850 Buddies = 2100 total to be consented).

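### Primary Aim 1(b), the percent reaching 7% weight loss, has no planned analysis, and the unqualified power statement in Section 1.3 holds only for mean weight

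*Combined protocol and SAP*

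**What the plan says.** Primary Aim 1 (Section 1.3) asks which components improve "a) average weight loss, and (b) percent achieving >7% weight loss among obese adults over a 6-month period". The primary research question (Section 3.1) has the same two parts, the second being "percent achieving $\geq 7\%$ weight loss among obese adults over a 6-month period". Section 1.3 then states: "We will use a highly efficient experimental strategy powered to detect effects of individual components as well as all two-way interactions". It does not say for which of the two outcomes.

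The later sections deal with weight alone:

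- **Outcome.** Section 4.2.2 is headed as the primary outcome and names weight.
- **Analysis.** Section 5 restates Primary Aim 1 as a test of differences in weight, using linear mixed models with component-by-time terms and 6 months as the primary endpoint.
- **Selection.** Step 1 (Section 5, Primary Aim 2) rests on "identification of the components that show a significant main effect on the primary outcome variable, weight". Step 2 considers interactions in the same model, and Step 3 uses its regression parameters.
- **Missing data.** Section 5.1 relies on the linear mixed model under missing at random (MAR), with sensitivity models. Section 5.4 carries the last assessment forward for participants who withdraw and will not return.
- **Power.** Section 5.2: "We base power on our primary endpoint: weight change from baseline to the 6-month timepoint".

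Outside the aim and the research question, 7% appears only as the participants' weight-loss goal and as a category for the letter to the primary care provider (both Section 4.4).

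**The concern.** Half of the stated primary question has no route to an answer. No section gives 1(b) a model, a place in the hierarchy, a power figure or a rule, written for this outcome, for classifying participants without a 6-month weight.

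If the responder result is reported anyway, as Aim 1 leads a reader to expect, the model and the treatment of dropouts would be chosen after the data are in. The choice matters because 10% attrition is expected. An MAR model, last observation carried forward, and counting dropouts as non-responders can each classify the same person differently against a threshold.

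A reader of Section 1.3 would also suppose that a non-significant responder result came from an adequately powered test. For a component that truly adds 1 kg, a non-significant result would be quite likely.

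**Working it through.** **Inputs from Section 5.2.** 560 randomized, 10% attrition, 504 at 6 months, 252 per level of each component; SD of weight change 4 kg; difference 1 kg (0.25 SD); two-tailed test; 80% power. Alpha is not stated. Two-sided 0.05 is inferred because it reproduces the sample size (one-sided 0.05 would need only 396 completers).

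**Step 1: reproduce the plan's figure.**
- n per level = 2 × (1.960 + 0.842)² / 0.25² = 251.2, rounded up to 252.
- Total 504, and 504 / 0.9 = 560.
- Power = Φ(0.25 × √(252/2) − 1.960) = Φ(2.806 − 1.960) = 80.1%.

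The plan's figure holds for weight.

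**Step 2: carry the same effect over to 7% response.** Take loss as normal with SD 4 kg and level means m − 0.5 and m + 0.5 kg. With baseline weight B, the threshold is 0.07B, and each proportion is p = 1 − Φ((0.07B − level mean) / 4). With p̄ the average of p₁ and p₂,

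Power = Φ{[(p₂ − p₁) − 1.960 × √(2p̄(1 − p̄)/252)] / √([p₁(1 − p₁) + p₂(1 − p₂)]/252)}.

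*Worked example (assumed B = 90 kg; m = 5.1 kg, the in-person mean loss cited in Section 2.1).* The threshold is 6.3 kg.
- p₁ = 1 − Φ((6.3 − 4.6)/4) = 1 − Φ(0.425) = 33.5%.
- p₂ = 1 − Φ((6.3 − 5.6)/4) = 1 − Φ(0.175) = 43.1%.
- Power = Φ((0.0951 − 1.960 × 0.0433) / 0.0431) = Φ(0.238) = 59%.

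**Step 3: avoid assuming baseline weight.** Under a 0.25 SD shift, power depends only on where the threshold falls, that is, on the mid-point responder rate:

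| Mid-point rate | Proportions | Power | Randomized for 80% power |
|---|---|---|---|
| 10% | 8.0% vs 12.4% | 37% | 1649 |
| 15% | 12.3% vs 18.1% | 45% | 1320 |
| 20% | 16.7% vs 23.7% | 50% | 1147 |
| 30% | 25.8% vs 34.5% | 56% | 974 |
| 40% | 35.3% vs 44.9% | 60% | 900 |
| 50% | 45.0% vs 55.0% | 61% | 880 |
| 67% | 62.4% vs 71.4% | 58% | 945 |

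The maximum is 60.8%, at a rate of 50%.

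**Step 4: ranges (assumed inputs).**
- Baseline 80-100 kg and mean loss 3-6.3 kg: 46% (100 kg, 3 kg) to 61%.
- At the cited mean losses of 4.6-5.1 kg: 55-61%.
- Baseline weight varying between people (SD 12-15 kg, mean 85-95 kg, mean loss 3-6 kg): 46-59%.
- Dropouts counted as non-responders, 280 per level, completer rates 20-50%: 49-57%.
- SD of 5 kg with the same 1 kg difference, baseline 80-100 kg, mean loss 3-6 kg: 35-43%.

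**The case against.** The strongest reply is that the hierarchy already exists. Sections 4.2.2, 5 and 5.2 all make weight the primary outcome, and 5.2 openly ties power to weight change. The sentence in Section 1.3 names no outcome, so it is loose wording and not a false claim. Section 5.4 would also give withdrawn participants a 6-month status. Much of this stands, and it is why relabelling 1(b) costs little. It does not give 1(b) an analysis, and Sections 1.3 and 3.1 still present it as half of the primary question. The carry-forward rule also conflicts with the MAR approach in 5.1, so it does not settle how responders would be classified.

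Three stronger readings are tempting but not supported:

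- **That component selection is compromised.** Steps 1-3 use weight only, so the chosen components and the $500 package do not depend on 1(b).
- **That without a responder analysis the trial cannot be set against its goal of results "comparable or superior to those achieved by the current full cost, full burden form of INLIs".** That goal concerns 6-month weight loss, and Section 2.1 reports intensive treatment as mean loss (4.6 and 5.1 kg), so mean weight is on the same scale. The figure in Section 1.1, a 5-8% loss in 50-67% of patients, is not a rate of reaching 7% and is no benchmark for 1(b). The plan sets no comparability test or margin.
- **That the population or threshold is wrong.** Aim 1 speaks of obese adults while entry is BMI 25-40, but this applies equally to 1(a), and Section 1.5 already plans analyses by BMI category. The more-than versus at-least 7% difference between 1.3 and 3.1 may come from reading the PDF; Section 4.4 says 7% or more. Both are minor wording points.

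**Conclusion.** The point holds as a conflict between the stated primary question and the stated analysis. Followed as written, the plan leaves 1(b) unanswered, and the power statement in Section 1.3 is true of weight only.

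The shortfall is from 80% to at most about 61%. That ceiling rests on the plan's own 1 kg, 4 kg SD and 252 per level, on two-sided 0.05, and on roughly normal weight loss with a common shift. It needs no assumption about baseline weight. The narrower range of about 46-61% does need one (80-100 kg, with mean loss 3-6.3 kg). Power falls further, to 45% or less, if the responder rate is 15% or lower. Conclusions about weight stand.

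**What to change.** 1. **Sections 1.3 and 3.1.** Label 7% response a secondary outcome, in line with Section 5, and write it as 7% or more in both places. Limit the power statement in 1.3 to 6-month weight change.
2. **Section 5.2.** State that power for response at the 1 kg effect is at most about 61%, with the assumptions shown.
3. **Section 5.** Add an analysis of 6-month response: a logistic model with the same effect-coded main effects and two-way interactions as the weight model, reported as risk differences with 95% confidence intervals. State that it plays no part in Steps 1-3.
4. **Sections 5.1 and 5.4.** Derive missing response status by multiple imputation of weight under the same MAR assumption as the mixed model. Reconcile this with the carry-forward rule in 5.4, so that the two outcomes do not rest on different treatments of the same missing weights.

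The cost is one extra model, some rewording and a less favourable power statement for 1(b). Keeping 1(b) as a co-primary outcome with 80% power would instead need at least 880 randomized at the same attrition (792 / 0.9), against the planned 560. Relabelling is therefore the practical course.

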1.5 Secondary Exploratory Aim

To improve understanding of how the five intervention components work and of differential response to intervention components by conducting analyses based on the data from the experiment in Primary Aim 1. The analyses will examine the following mediators of weight loss: (a) hypothesized: adherence to treatment, and (b) exploratory: social-cognitive variables (self-efficacy, self-regulation, supportive accountability, and facilitation). To investigate whether certain intervention components are more or less effective in certain subgroups, we will examine moderation by conducting analyses separately for subgroups defined by gender, ethnicity, and BMI categories. We will also conduct latent class analysis to identify latent subgroups and predictors of subgroup membership. The results will inform subsequent research aimed at developing interventions tailored and optimized for these subgroups.

2 Background

2.1 Significance

The World Health Organization reports that more than one billion adults globally exceed healthy body weight. In the U.S. in 2007, 30% of the adult population was obese, double the rate in 1980 (Flegal et al., 2010). Currently, more than 69% of U.S. adults are either overweight or obese (Flegal et al., 2012). Obesity is an expensive condition because of its association with chronic disease. U.S. obesity-attributable medical expenditures are estimated at \$75 billion annually, with \$17 billion financed by Medicare and \$21 billion financed by Medicaid (Finkelstein et al., 2004). Given the U.S. obese population of 60 million, this yields annual obesity-attributable medical expenditures of \$1,250 per obese individual. Effective weight loss interventions have the potential to reduce the risk of chronic diseases, and save millions of health care dollars. Yet the most effective intensive lifestyle interventions (INLIs) are not accessible to most people because they have not been viewed as feasible for widespread implementation.

The most extensively studied INLIs for weight loss are the multi-session, in-person Diabetes Prevention Program (DPP) (2002), and related Action for Health in Diabetes (Look AHEAD) (2007). Although both have proved strongly efficacious in multi-site randomized controlled clinical trials (RCTs), neither these programs nor any other INLI has been widely adopted because they are considered too burdensome and expensive to be sustainable (Eddy et al., 2005). The weight loss initiation phase of most INLIs requires at least 16 in-person, face-to-face sessions with a specialist and costs about \$1400/year per patient (DPP, 2002). Cost can be reduced below \$500 per participant by training YMCA staff to deliver the program (Ackermann et al., 2008; Ackermann & Marrero, 2007), but that requires patients to have access, willingness, and ability to go to a Y to attend multiple sessions. The other popular INLI implementation strategy has been to reduce cost by lowering treatment intensity (i.e., decreasing the number of sessions). However, that approach has yielded mixed results (Mau et al., 2010; Whittemore, 2011; Whittemore et al., 2009). Reducing intensity sacrifices opportunities for feedback and accountability, and usually leads weight loss to diminish as frequent face-to-face meetings are pruned back (Davis-Smith et al., 2007). The still unmet challenge of INLI implementation is how to reduce treatment burden, intensity, and cost without eliminating intervention components that are essential to successful weight loss.

The importance of the proposed research lies in the objective to reconfigure weight loss treatment so as to achieve the intended outcome more efficiently and in a manner that allows greater reach. New technologies now make it feasible to deliver treatment and support behavior change from a distance, reducing the need for burdensome in-person contact. A recent comparative effectiveness trial by Appel and colleagues (2011) demonstrated that a technology-supported INLI that delivers lessons via the web and coaching via telephone can be as effective for fostering weight loss as a traditional in-person delivery method. In that study, those randomized to receive 33 telephone coaching sessions lost approximately as much weight as those receiving in-person support (-4.6kg vs. -5.1kg). Because costs for trained personnel are the most expensive part of any INLI, more efficient treatment requiring fewer sessions would be highly advantageous. An optimized treatment could have a reduced number of sessions (e.g., 12 calls able to be delivered by paraprofessionals), but acquire increased impact by adding other low-cost active components. Several candidate components exist, but none has a known, quantified impact independent of other bundled treatment elements. For example, text messaging for obesity treatment has been bundled with telephone coaching (Patrick et al., 2009; Shrewsbury et al., 2009). Informing the primary care provider (PCP) about the patient's weight loss progress has been confounded with having the physician provide behavioral weight loss treatment or having allied health professionals deliver treatment in high-cost medical space, neither of which is cost-efficient (Wadden et al., 2011; Institute of Medicine [IOM], 2010). Other components, e.g., meal

replacements, have been tested in such expensive formats (e.g., free food provision) as to preclude real world implementation (Look AHEAD, 2007; Wadden et al., 2011). Another example involves the use of peers to provide social support who are given so much training (e.g., 36 hours) that they can more aptly be described as semiprofessionals (Katula et al., 2011).

The proposed research is significant in representing the first principled and systematic effort to design a weight loss treatment that is as effective and efficient as possible, such that all of its components are active, feasible for real world implementation, and make the lowest possible resource demands. The resulting treatment will be readily scalable and will support significant progress in the fight against obesity.

